Statistical analysis will be performed using SAS software Version 9.4 or later. Continuous variables will be summarised using the mean, standard deviation, median, minimum value, and maximum value. Categorical variables will be summarised using frequency counts and percentages. Data will be listed in data listings.

Details of the statistical analyses, methods, and data conventions will be described in the statistical analysis plan (SAP). All statistical tests will be 2-sided and performed using a 5% significance level, leading to 95% (2-sided) confidence intervals (CIs), unless indicated otherwise.

Analysis of Primary Efficacy Endpoint

Main Estimation of Primary Efficacy Estimand 1

The primary efficacy estimand is the absolute difference between each of the 3 different doses of MBS2320 and placebo in the percentage of participants who would achieve successful composite clinical response at Week 12 (which assumes failure for those who have any increase in RA medications or treatment discontinuation due to lack of efficacy or tolerability issues). The primary efficacy estimand will be estimated using a logistic regression model and the delta method, with the stratification factors and treatment as factors using the mFAS (Flag P). Missing data will not be imputed and are assumed missing completely at random (MCAR).

Sensitivity Analysis of Primary Efficacy Estimand 1

In the sensitivity analysis of the primary efficacy estimand, multiple imputation (MI) assuming missingness at random (MAR) will be used to impute any missing component of the composite clinical response at Weeks 4, 8, and 12, and then to derive the composite

outcomes. The logistic model will be fitted to each multiply imputed data set and the estimates of difference in percentages and standard error (SE) from the delta method will be pooled using Rubin's method. The overall difference of each dose relative to placebo will be presented with *P* value.

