Also, in order to further study the successful composite clinical response profile across active doses, an additional sensitivity analysis will be conducted for studying the dose response relationship among the 3 MBS2320 doses and placebo dose. A logistic model will be fitted to multiply imputed data sets with dose in mg as a continuous variable to assess the trend across dose, including placebo as zero dose (i.e. placebo=0 mg dose level and dose levels of 5 mg, 20 mg, and 40 mg). The slope with CI and *P* value will be pooled using Rubin's method.

Analysis of Key Secondary Efficacy Endpoints

Main Estimation of Secondary Efficacy Estimand 2A

The first key secondary efficacy estimand (Estimand 2A) is based on the difference in mean change in Rheumatoid Arthritis Magnetic Resonance Imaging Score (RAMRIS) score from baseline to Week 12, as though no increase in any other RA medication and no treatment discontinuation for any reason, in patients with MBS2320 (5 mg, 20 mg, or 40 mg once daily) compared to placebo.

All assessments after any of the intercurrent events will be censored. An MI model will be used to impute any missing (or censored) score at Week 12 assuming MAR. The RAMRIS score and change from baseline in RAMRIS score will be derived on each multiply imputed data set and analysed using analysis of covariance (ANCOVA) with fixed effect terms for treatment and stratification factors, and baseline RAMRIS score as covariate. Rubin's method will be used to pool results so that the differences in mean change in RAMRIS score can be presented with 95% CI and *P* value.

Estimation of Supportive Efficacy Estimand 2B

Estimand 2B is defined as the difference in mean change in RAMRIS score from baseline to Week 12 in patients with MBS2320 (5 mg, 20 mg, or 40 mg once daily) compared to

placebo, irrespective of treatment discontinuation or interruption due to tolerability issues or lack of efficacy and as though no increase in any other RA medication. Data after all intercurrent events except discontinuation or interruption of treatment due to tolerability issues or lack of efficacy will be censored. Data missing for reasons unrelated to treatment (e.g. participant not willing to undergo MRI scan) will be imputed under the MAR assumption.

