A reference-based multiply imputation model will be used to impute missing data after discontinuation of treatment due to related reasons (tolerability issues or lack of efficacy). As for Estimand 2A, the change from baseline in RAMRIS score will be derived on each multiply imputed data set and analysed using ANCOVA, and Rubin's method will be used to pool results.

Main Estimation of Secondary Efficacy Estimand 3A

A mixed model for repeated measures (MMRM) will be fitted to change from baseline at Weeks 4, 8, and 12 as the dependent variable and including fixed effects for DAS28-hsCRP baseline covariate, treatment, visit, treatment by visit interaction, and the stratification factors. An unstructured covariance will be used to model the covariances over time on participants. The least squares mean change from baseline in DAS28-hsCRP and differences relative to placebo with 95% CI and *P* value will presented at each time point.

Missing data are assumed to be MAR in the MMRM, which is well suited to estimate this type of hypothetical estimand.

Main Estimation of Secondary Efficacy Estimand 3B

Similar estimation (via MMRM) as described for Estimand 3A will be conducted for Estimand 3B. Note that this requires participants who discontinue treatment to return at Week 12 for assessment. Missing data are assumed to be MAR, which is unlikely to hold in the case of dropouts following discontinuation of treatment.

A sensitivity analysis will be conducted for Estimand 3B, using a reference-based MI model to impute missing data after discontinuation due to related reasons. The change from baseline

in DAS28-hsCRP will be derived on each multiply imputed data set and analysed using MMRM, and Rubin's method will be used to pool results.

Main Estimation of Secondary Efficacy Estimand 4

The estimation of Estimand 4 is similar to that described for Estimand 1. A logistic model will be fitted to successful composite clinical response at each of Weeks 4 and 8 including the stratification factors and treatment (qualitative) as factors; missing data will not be imputed and assumed MCAR.

In a sensitivity analysis, an MI model will be used to impute any missing components of the composite clinical response at Weeks 4, 8, and 12. Logistic model will be fitted to each multiply imputed data set and Rubin's method use to pool results. The overall difference of each dose relative to placebo will be presented with *P* value, at each time point.

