Additional sensitivity analysis of the successful composite clinical response at Weeks 4, 8, and 12 will be performed using Logistic Generalized Linear Mixed Model with fixed effects for treatment, visit, treatment by visit interaction, and the stratification factors. More details will be provided in the SAP.

Analyses of Other Efficacy and Exploratory Endpoints

The other efficacy endpoints will be analysed descriptively, based on the mFAS (Flag B), except for ordinal endpoints (e.g. ACR50 & ACR70) which will be analysed based on mFAS (Flag P). Sensitivity analysis may be undertaken; details will be provided in the SAP.

The exploratory efficacy endpoints will be analysed descriptively, based on the mFAS (with no flags applied) and the mFAS (Flag A). Sensitivity analysis may be undertaken; details will be provided in the SAP.

Analysis of Pharmacokinetic Endpoints

MBS2320 and MBS2473 plasma concentrations will be determined in pre-dose samples at Weeks 4 and 12, postdose samples collected 3 (± 1) hours following last dose at Week 12, and at EOS.

Plasma concentration of MBS2320 and MBS2473 (where applicable) will be determined for each sample, excluding placebo controls.

All MBS2320 and MBS2473 plasma concentration data will be listed by participant and visit/sampling time point and summarised by administered treatment.

SAS® software Version 9.4 or higher (SAS Institute, Inc, Cary, North Carolina) will be utilised for the generation of any tables, listings, and figures.

Analyses of Safety

The incidence of treatment-emergent AEs for the safety population will be summarised by treatment group. Adverse events will be coded using the Medical Dictionary for Regulatory Activities to classify events under primary system organ class and preferred term. Adverse event data will be presented in incidence tables. Adverse events will also be summarised by severity, seriousness, and relationship to IP for each treatment group. Data will also be listed in data listings.

The incidence of laboratory abnormalities by type, frequency, and severity will be summarised by treatment groups. Change from baseline in continuous laboratory variables will be summarised by visit and treatment groups.

All other safety variables (including vital signs and ECGs) will be summarised by treatment group and visit.

Other Analyses

Summary statistical analyses will be provided for demographics, medical history, and physical examination, and ophthalmological assessments at baseline.

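### The dose-trend logistic model names dose in mg as its only term; the plan should state that it carries the same stratification factors as the main Estimand 1 model.

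*Combined protocol and SAP*

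**What the plan says.** All places are in the Protocol Synopsis, Statistical Methods.

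- **Trend model** (Sensitivity Analysis of Primary Efficacy Estimand 1, second part): "A logistic model will be fitted to multiply imputed data sets with dose in mg as a continuous variable to assess the trend". The dose scores are "placebo=0 mg dose level and dose levels of 5 mg, 20 mg, and 40 mg". The output is a log-odds slope per mg: "The slope with CI and *P* value will be pooled using Rubin's method". No other model term is named, and nothing refers back to the main model.
- **Main Estimand 1 model**: a "logistic regression model and the delta method, with the stratification factors and treatment as factors".
- **Estimand 2A ANCOVA**: treatment, stratification factors and baseline RAMRIS.
- **Estimand 3A MMRM**: lists the stratification factors with treatment, visit, their interaction and baseline.
- **Estimand 4 main model**: "including the stratification factors and treatment (qualitative) as factors".
- **Mixed logistic model** (additional sensitivity analysis for Estimand 4): fixed effects for "treatment, visit, treatment by visit interaction, and the stratification factors".
- **Models that do not restate their terms**: the first Estimand 1 imputation analysis, Estimand 2B and Estimand 3B each point back to a model that has the factors. The Estimand 4 imputation sensitivity model names no covariates, and only its context ties it to the main model.

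The synopsis gives a 1:1:1:1 ratio. It does not name the stratification factors, count them or describe how randomisation was stratified. It leaves analysis detail to the SAP.

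**The concern.** When randomisation is stratified, the strata are balanced across the arms, so differences between strata cannot move the slope. A model that leaves the strata out still counts that variation as noise in its model-based SE. If the strata predict response, the SE is too large, the interval too wide, and the test rejects less often than 5% under the null. There is a second effect: log-odds coefficients are non-collapsible, so leaving out a prognostic factor gives a slope nearer zero than the within-stratum slope.

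This is a dose-ranging trial, and the trend model is the one place where the synopsis relates the primary endpoint to dose as a quantity. A programmer following the sentence literally would fit dose alone; one who assumes that the main model's terms carry over would not. The two give different P values from the same data, so the choice should be fixed before unblinding.

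**Working it through.** **1. The plan's own figure.** No figure is given for the trend test, so I checked the sample size that it would use. Inputs from Sample Size: 35% v 65%, two-sided 5%, 80% power, about 45 evaluable per arm (180), 224 randomised, 20% loss.

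n per arm = [1.96·√(2·0.5·0.5) + 0.8416·√(2·0.35·0.65)]² / 0.30² = (1.386 + 0.568)² / 0.09 ≈ 42.4, so 43. With 45 per arm, power is 82.4%. 180 / 0.8 = 225 against 224 stated. The figures reproduce.

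**2. Assumption.** The documents give no prognostic strength. Range used: one or two balanced binary factors, each with an outcome odds ratio (OR) of 1 to 4.

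**3. Large-sample size of the unadjusted test.** Under the null at 35% response, let r = (mean within-stratum variance) / (0.35 × 0.65). The SE is overstated by 1/√r, and the true size is 2·[1 − Φ(1.96/√r)].

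Example, one factor, OR 2: the stratum rates are 0.272 and 0.428. Mean within-stratum variance = (0.272·0.728 + 0.428·0.572)/2 = 0.2214; r = 0.2214/0.2275 = 0.973; 1.96/√0.973 = 1.987; size = 4.7%.

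| Factors, OR each | r | SE overstated by | Size |
|---|---|---|---|
| any, OR 1 | 1.000 | 0% | 5.0% |
| one, OR 2 | 0.973 | 1.4% | 4.7% |
| one, OR 4 | 0.901 | 5.3% | 3.9% |
| two, OR 2 | 0.949 | 2.6% | 4.4% |
| two, OR 4 | 0.831 | 9.7% | 3.2% |

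**4. Simulation.** 180 patients, permuted blocks of 4 within strata, doses 0/5/20/40 mg, Wald test of the slope, complete data, 8,000 null and 3,000 alternative trials. Under the alternative, the overall response rate rises linearly on the logit from 35% at 0 mg to 65% at 40 mg. Each cell is unadjusted v adjusted.

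| Factors, OR each | Size | Power | Mean slope per mg |
|---|---|---|---|
| one, OR 1 | 4.7% v 4.8% | 89.5% v 89.5% | 0.0319 v 0.0321 |
| one, OR 2 | 4.6% v 4.9% | 89.9% v 90.5% | 0.0317 v 0.0328 |
| one, OR 4 | 3.9% v 5.0% | 89.6% v 91.4% | 0.0313 v 0.0354 |
| two, OR 2 | 4.3% v 4.8% | 90.4% v 91.7% | 0.0317 v 0.0340 |
| two, OR 4 | 3.2% v 5.6% | 91.0% v 93.7% | 0.0311 v 0.0384 |

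The unadjusted slope is smaller by 1 − 0.0317/0.0328 ≈ 3% (one factor, OR 2) up to 1 − 0.0311/0.0384 ≈ 19% (two factors, OR 4).

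**5. Sensitivity to how the alternative is set.** Step 4 holds the overall arm rates fixed. I also held the within-stratum slope fixed at 2·ln(0.65/0.35)/40 = 0.031 per mg, with 176 patients exactly balanced within strata and 20,000 trials per setting. Power was 86.5% v 87.1% (one factor, OR 2), 81.5% v 84.6% (one factor, OR 4) and 75.3% v 81.7% (two factors, OR 4). The last is a loss of 6.4 points. The size of the adjusted test was 4.9% to 5.1% throughout, including 4.9% for two factors with OR 4, so the 5.6% in step 4 did not recur. Another run of this design gave a size of 4.4% v 4.8% for one factor with OR 2.

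None of these runs included the multiple imputation that the plan specifies.

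**The case against.** The strongest reply is that the text is silent; it does not exclude the factors. The trend analysis sits under the Estimand 1 sensitivity heading, straight after a model that inherits the main model's terms. It can be read as changing only how treatment is coded. The synopsis also leaves detail to the SAP. This stands: the point is under-specification, and the documents do not show that an unadjusted test is intended. It does not remove the point, because the sentence introduces a new model, with an indefinite article and no pointer back.

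Three stronger readings are tempting, and the documents support none of them.

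- *That this is the only between-arm model without the factors.* The Estimand 4 imputation model also names no covariates, and the reference-based Estimand 3B analysis does not restate its own.
- *That the slope test is conservative, without qualification.* That needs stratified randomisation, which is implied but never described, and prognostic factors, on which there are no data. With OR 1 the effect vanishes.
- *That the omission puts the slope on a different scale from the main result.* The main result is a difference in percentages: "The primary efficacy estimand is the absolute difference between each of the 3 different doses of MBS2320 and placebo in the percentage" of responders. The trend is a log-odds slope, and the two stay on different scales after the fix. Adding the factors removes only the marginal-versus-conditional difference between log-odds coefficients. The unadjusted slope is a valid marginal quantity and is not biased.

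It is also fair to say that little depends on this. It is an additional sensitivity analysis, no sample size or stated decision rule uses it, and the possible error is towards caution.

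**Conclusion.** The point holds as a low-severity specification gap. Where the synopsis spells out the terms of its other between-arm models, the stratification factors are there; in the trend model only dose is named.

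If the model is fitted that way after randomisation stratified by prognostic factors, the effects are small and all in one direction:

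- size of about 4.4% to 4.7% for one factor with odds ratio 2, and about 3% to 4% for stronger or two factors;
- a power loss of roughly 0.5 to 3 points, reaching about 6 only with two strong factors and a fixed within-stratum slope;
- a log-odds slope about 3% to 19% smaller.

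These figures rest on assumed factor strength and on complete data. With non-prognostic factors there is no effect. The direction is standard theory and agrees across the formula and the simulations; the size in this trial cannot be known from the documents.

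**What to change.** In the dose-response part of Sensitivity Analysis of Primary Efficacy Estimand 1, say that the logistic model includes the same stratification factors as the main Estimand 1 model, with dose in mg entered as a continuous variable. Say the same for the multiple-imputation logistic model under Estimand 4, with treatment as a factor. Carry both statements into the SAP before unblinding.

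The cost is one phrase in each place and the extra model terms. The trend model would still have two fewer parameters than the main model already planned (one dose term in place of three treatment contrasts), so it adds no fitting difficulty that the main model does not already face. If the factors turn out not to predict response, the simulations show no measurable loss of power (89.5% either way for one factor with odds ratio 1).

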Estimand 2A: Difference in mean change from baseline in each RAMRIS score (synovitis, bone oedema, and bone erosion scores, measured with MRI), in patients with moderate to severe active RA and a previous inadequate response to MTX alone, with confirmed intraarticular synovitis on

Estimand 2B: Difference in mean change from baseline in each RAMRIS score (synovitis, bone oedema, and bone erosion scores, measured with MRI), in patients with moderate to severe active RA and a previous inadequate response to MTX alone, with confirmed intra-articular synovitis on

Key Secondary Objectives

To evaluate the efficacy of MBS2320 (5 mg once daily, 20 mg once daily, and 40 mg once daily) compared with placebo on other clinical endpoints in participants with active RA on stable background MTX who have had an inadequate response to MTX alone, with confirmed intra-articular synovitis on baseline MRI.

Objectives

Estimand Description (Including Endpoint)

baseline MRI, assessed after 12 weeks of treatment with MBS2320 (5 mg, 20 mg, or 40 mg once daily) compared to placebo (each on top of stable background RA medication of weekly MTX), as though no increase in any RA medication and no treatment discontinuation or interruption for any reason.

baseline MRI, assessed after 12 weeks of treatment with MBS2320 (5 mg, 20 mg, or 40 mg once daily) compared to placebo (each on top of stable background RA medication of weekly MTX), irrespective of treatment discontinuation or interruption due to tolerability issues or lack of efficacy, and as though no increase in any other RA medication.

Endpoint: Change in DAS28-hsCRP from baseline to Weeks 4, 8, and 12.

Estimand 3A: Difference in mean change from baseline in DAS28-hsCRP in patients with moderate to severe active RA with a previous inadequate response to MTX alone, with confirmed intra-articular synovitis on baseline MRI, after each of 4, 8, and 12 weeks of treatment with MBS2320 (5 mg, 20 mg, or 40 mg once daily) compared to placebo (each on top of stable background RA medication of weekly MTX), as though no increase in any RA medication and no treatment

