group participants according to the treatment they actually receive.

Full Analysis Set

The FAS will consist of all randomised participants whether or not they experienced significant protocol deviations affecting evaluations.

they experienced significant protocol deviations affecting evaluation of the endpoints. All analyses using the FAS will group participants

according to the randomised treatment.

Modified Full Analysis Set (mFAS) The mFAS will consist of all randomised and eligible participants with confirmed intra-articular synovitis on baseline MRI in FAS (grouped according to randomised treatment). The mFAS applies analysis flags to censor data after certain intercurrent events:

Flag P: Censors data after discontinuation or interruption of treatment for unrelated reasons (i.e. due to logistical issues or AEs due to an unrelated medical condition not considered to be due to treatment or the underlying RA disease) and resulting in >20% reduction in treatment administered during the approximately 4-week period since last visit. If treatment is resumed following an interruption, then subsequent data may be included provided at least 80% of treatment is taken during the previous 4-week period. This will be particularly useful for targeting Estimands 1 and 4.

Flag A: Censors data after discontinuation or interruption of treatment for any reason or any increase in RA medications and will be particularly useful for targeting hypothetical estimands (Estimands 2A and 3A). Only interruptions resulting in >20% reduction in treatment administered during the approximately 4-week period since last visit are considered relevant; for shorter interruptions, all resulting data are selected. If treatment is resumed following an interruption, then subsequent data may be included provided at least 80% of treatment is taken during the previous 4-week period.

Flag B: Censors data after discontinuation of treatment for unrelated reasons or any increase in RA medications and will be particularly useful for targeting the 'partially' hypothetical estimands (Estimands 2B and 3B). Interruptions for unrelated reasons are handled in the same way as Flag P.

Pharmacokinetics (PK) Set

The PK set will consist of all participants who receive at least 1 dose of MBS2320 and have at least 1 evaluable PK concentration. Analyses using the PK population will group participants according to treatment received.

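### The DAS28-hsCRP MMRM assumes one baseline slope at Weeks 4, 8 and 12; adding baseline-by-visit guards against a small loss of precision and a small conditional bias

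*Combined protocol and SAP*

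**What the plan says.** Under Statistical Methods, the paragraph on the main estimation of Estimand 3A states: "A mixed model for repeated measures (MMRM) will be fitted to change from baseline at Weeks 4, 8, and 12 as the dependent variable". The fixed effects are given as "including fixed effects for DAS28-hsCRP baseline covariate, treatment, visit, treatment by visit interaction, and the stratification factors". On the covariance: "An unstructured covariance will be used to model the covariances over time on participants". No interaction between baseline and visit is listed there or elsewhere in the supplied text.

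The next paragraph carries the model over: "Similar estimation (via MMRM) as described for Estimand 3A will be conducted for Estimand 3B". A sensitivity analysis for 3B imputes data with a reference-based model and then analyses the imputed sets by MMRM.

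The endpoint is key secondary, "Change in DAS28-hsCRP from baseline to Weeks 4, 8, and 12", with differences from placebo, 95% CI and P value reported at each visit. For 3A the missing-data position is: "Missing data are assumed to be MAR in the MMRM, which is well suited to estimate this type of hypothetical estimand". Much of the missingness will come from Flag A, which "Censors data after discontinuation or interruption of treatment for any reason or any increase in RA medications".

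The Statistical Methods section leaves further detail to the SAP. The supplied text contains only this synopsis-level description of the model.

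**The concern.** The model is flexible in treatment-by-visit and covariance but rigid in baseline. For a change score, the slope on baseline at visit t is

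β_t = ρ_t × SD_t / SD_0 − 1,

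where ρ_t is the correlation of the visit-t score with baseline. A single slope is right only if ρ_t × SD_t is the same at Weeks 4, 8 and 12, and nothing in the documents suggests that it is. If it is not, the pooled slope fits Week 12 imperfectly.

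Two things follow. Baseline variation that could have been removed stays in the Week 12 comparison, which widens its SE. And if those still observed at Week 12 have a different baseline mix in each arm, the misfit can leak into the treatment difference. By contrast, the RAMRIS analysis for Estimand 2A is a Week 12 ANCOVA, so its baseline slope is already specific to Week 12.

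**Working it through.** **The plan's own figure.** The only sample-size figure is for the primary endpoint: 35% v 65%, two-sided 5%, 80% power, about 45 per arm. A Wald test on the log odds ratio gives ln OR = 2 × ln(0.65/0.35) = 1.238, variance term 2/(0.35 × 0.65) = 8.791, and n = (1.960 + 0.842)² × 8.791 / 1.238² = 45.0 per arm. Inflating for 20% loss, 180/0.8 = 225 against about 224 stated. Both reproduce. No power, SD or slope is given for DAS28-hsCRP.

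**Precision, complete data.** Let Σ be the residual covariance of the three visits. The common-slope fit settles on b = 1′Σ⁻¹β / 1′Σ⁻¹1. The Week 12 difference then has variance

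(2/n) × [σ²₁₂ + SD_0² × (β₁₂ − b)²].

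With baseline-by-visit the second term vanishes. Assume SD 1 at baseline and every visit, and between-visit correlation 0.65, so that σ²₁₂ = 1 − ρ₁₂²:

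| Assumed ρ at Weeks 4/8/12 | β₁₂ | b | (β₁₂ − b)² | σ²₁₂ | Variance saved |
|---|---|---|---|---|---|
| 0.55/0.50/0.45 | −0.55 | −0.493 | 0.0032 | 0.7975 | 0.4% |
| 0.60/0.50/0.40 | −0.60 | −0.470 | 0.0169 | 0.84 | 2.0% |
| 0.60/0.45/0.30 | −0.70 | −0.484 | 0.0467 | 0.91 | 4.9% |
| 0.70/0.45/0.20 (extreme) | −0.80 | −0.300 | 0.2500 | 0.96 | 20.7% |

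A 4.9% saving in variance is 1 − √0.951 = 2.5% in SE. The third row moves with the between-visit correlation. At 0.75 throughout, b = −0.451 and the saving is 0.0620/0.972 = 6.4%. At 0.65 between adjacent visits, decaying to 0.65² = 0.4225, b = −0.512 and it is 0.0353/0.945 = 3.7%.

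If the SDs instead rise as 1.0/1.1/1.2, the first three rows have slopes of −0.45/−0.45/−0.46, −0.40/−0.45/−0.52 and −0.40/−0.505/−0.64, and the savings fall to about 0%, 0.8% and 3.4%.

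**Precision at trial size.** Simulation with 45 per arm, four arms and 1,000 trials per scenario assumed baseline SD 0.9, residual SDs 1.0/1.1/1.2 and correlation about 0.65, without stratification factors. The ratio of Week 12 SDs, common slope over interaction, was:

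- slopes equal at −0.4: 1.00
- −0.3/−0.4/−0.5: 1.00 to 1.01
- −0.2/−0.35/−0.5: 1.01 to 1.02
- −0.1/−0.4/−0.7, a very wide swing: 1.03 to 1.05

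With equal slopes, adding the interaction raised the mean SE by at most about 1% (for example 0.2845 to 0.2874).

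**Bias.** Large-sample fits of both models gave, for common slope minus interaction at Week 12:

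- no dropout, MCAR dropout or equal slopes: about 0
- slopes varying, one MAR rule shared by all arms: at most about 0.01 DAS28 units
- slopes varying, MAR dropout driven by earlier disease activity: 0.002 to 0.010 SD with 18% v 13% missing, and 0.004 to 0.018 SD with 24% v 16%
- slopes varying, dropout depending on baseline differently by arm (about 27% v 18%): 0.03, 0.05 and 0.09 DAS28 units for the three varying-slope sets above
- a deliberately extreme version of the last (about 34% v 20%): 0.06, 0.10 and 0.20

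For scale, √(2/45) = 0.21 SD, so 0.018 SD is about 9% of one SE. In DAS28 units the simulated SE was about 0.28, so 0.03 to 0.09 is 11% to 32% of one SE. Coverage stayed at 94 to 95% under the differential rule and fell to 91% only in the extreme case with the widest slopes. With baseline-by-visit included, the bias was within simulation error of zero throughout.

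**The case against.** The best case for leaving the model alone has several parts.

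- **Fading correlation is not enough.** A reader might infer that because correlation with baseline fades, the slope must steepen by Week 12. It need not. With baseline SD 0.9, residual SDs of 1.0 and 1.2 at Weeks 4 and 12, and a slope of −0.4 at every visit, the correlation is 0.54/√(0.54² + 1.0²) = 0.475 at Week 4 and 0.54/√(0.54² + 1.2²) = 0.410 at Week 12, with no slope change at all. This stands.
- **Dropout alone does not bias the difference.** A reader might also infer that the Week 12 result is biased towards the drug. The documents do not support that: bias needs slopes that vary by visit together with differential dropout, and they show neither. The simulated bias favoured active treatment, but its sign depends on the pattern. Flag A makes differential censoring plausible, no more.
- **The effect is small and the term is not quite free.** The gain under mild to moderate slope changes is of the same order as the 1% cost when slopes are equal. This stands too, and limits the point to an inexpensive improvement.
- **The bias argument does not extend to the 3B sensitivity analysis.** There the MMRM is fitted to imputed data, so only a small precision gain remains. For 3B itself, the plan's own admission that MAR is unlikely after discontinuation is the larger issue.
- **The SAP may add detail.** It may. But the list of terms is explicit, and an SAP author following it would fit the common slope.

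**Conclusion.** The point holds as a minor, conditional one. As written, the MMRM for 3A and 3B imposes a common baseline slope that the documents give no reason to expect. Under assumed mild to strong falls in correlation with equal SDs, the cost at Week 12 is about 0 to 5% in variance (0 to 2.5% in SE), and less if the SD rises. It exceeds this only under very wide swings in slope. Bias is about 0.002 to 0.02 SD when slopes vary and disease-related MAR dropout differs by arm. It reaches 0.03 to 0.09 DAS28 units, or more in an extreme case, only if dropout depends on baseline differently by arm.

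Every one of these sizes rests on assumed correlations, SDs, slopes and dropout. None of this makes the planned analysis invalid.

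**What to change.** In the SAP, before unblinding, add the baseline DAS28-hsCRP-by-visit interaction to the MMRM for Estimands 3A and 3B. Use the same analysis model on the imputed data sets in the 3B sensitivity analysis, for consistency.

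The cost is one model term (two degrees of freedom with three visits) and the small SE penalty shown above if the slopes turn out to be equal. It needs no extra participants, visits or data.
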